### 4.3 Analyses of secondary endpoints

The analysis of secondary endpoints will be used for hypothesis generation/signal detection. We will calculate crude incidence and 95% CI for each secondary endpoint for the exposed and unexposed cohorts. Unadjusted and adjusted RR with two-sided 95% CI will be estimated comparing the exposed cohort to the unexposed cohort. At least one case in each cohort is required to perform unadjusted and adjusted analyses. If total counts from the two groups is less than 5, then no adjusted analysis will be performed. An elevated risk will be detected if the lower limit of the 95% CI for the adjusted relative risk is above 1. The planned methods of analysis by secondary endpoint are outlined in Table 5. See Appendix A, Table Shell 4 for details.

Table 5. Analytic population and statistical methods by secondary endpoint

Secondary endpoints	Analytic population	Statistical Methods
Transfusion during delivery hospitalization	Pregnant women with delivery hospitalization	Adjusted Poisson regression model
Poor fetal growth	All pregnant women eligible for main analysis	Adjusted Poisson regression model accounting for follow up time, with robust variance estimate
Stillbirth/fetal death*	Pregnant women with pregnancy outcome	Adjusted Poisson regression model
Neonatal death	KPSC live born infants	Adjusted Poisson regression model
Maternal death	All pregnant women eligible for main analysis	Adjusted Poisson regression model accounting for follow up time
Placental abruption	All pregnant women eligible for main analysis	Adjusted Poisson regression model accounting for follow up time
PPROM	All pregnant women, with index (vaccination) date prior to 37 weeks gestation	Adjusted Poisson regression model accounting for follow up time
Congenital anomalies (CA) by type	KPSC live born infants	Adjusted Poisson regression model, with robust variance estimate if outcome is common

\*Stillbirth/fetal death will be described with or without congenital anomalies separately, but will be analyzed as one outcome.

For poor fetal growth, placental abruption, PPROM, and maternal death, the incidence will consist of the total number of women with the condition in the numerator and the total person time in the denominator. For poor fetal growth, placental abruption, and PPROM, the person-time for a pregnant woman will be the time from the index date to the date of each adverse event, end of the pregnancy, or disenrollment, whichever comes first. For maternal death, the person-time for a pregnant woman will be the time from the index date to the date of death, 42 days after delivery, or disenrollment, whichever comes first. The unadjusted and adjusted relative risk with 95% CI will be estimated by Poisson regression models, or Poisson regression models with robust error variances if incidence >2%, accounting for the follow-up time without and with adjustment for potential confounders.

For stillbirth/fetal death and transfusion during delivery hospitalization, the incidence will consist of the total number of women with the condition in the numerator and the number of women for whom the condition can be assessed in the denominator. The unadjusted and adjusted relative risk with 95% CI will be estimated by Poisson regression models, without and with adjustment for potential confounders.

Neonatal death and congenital anomalies will be identified among infants born in KPSC hospitals. The incidence of neonatal death will be calculated as the number of neonatal deaths in the numerator and the total number of infants born in KPSC hospitals in the denominator. The prevalence of congenital anomalies (overall, by type) will be calculated as the number of infants with a congenital anomaly in the numerator and the total number of infants born in KPSC hospitals in the denominator. The proportion of live births without congenital anomalies will be calculated as 1 minus the proportion of live births with congenital anomalies among all KPSC live born infants. The unadjusted and adjusted relative risk with 95% CI will be estimated by Poisson regression models, or Poisson regression models with robust error variances if incidence >2%, without and with adjustment for potential confounders.

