## 4.5 Signal investigation

If a primary endpoint analysis cannot rule out a 2-fold relative risk, or secondary endpoint analysis detects an elevated risk, further exploration of the data will be completed to investigate alternative potential sources for the Boostrix-outcome association.

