### 5.2 Multiplicity considerations

Analyses of the primary endpoints will be conducted using a non-inferiority design with multiple comparison adjustment. Analyses of the secondary endpoints will be conducted using superiority testing without adjustment for multiple comparisons. The approach leads to a more conservative

conclusion regarding safety of vaccination, i.e., for a non-inferiority test, it is harder to reject  $H_0: RR \geq 2$ , and for a superiority test, it is easier to reject  $H_0: RR = 1$ .

The analyses of secondary endpoints will be used for hypothesis generation/signal detection. No formal adjustment for multiple comparisons is common practice for this type of study. Since outcomes monitored in vaccine safety studies are usually serious, researchers do not want to miss the opportunity to detect potential safety findings.

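### The SAP gives no pre-specified signal trigger for a rare secondary outcome with six or more cases in the vaccinated cohort and none in the unvaccinated cohort

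*SAP*

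**What the plan says.** SAP 4.3 gives the purpose of these analyses: "The analysis of secondary endpoints will be used for hypothesis generation/signal detection". It then sets two sparse-data limits. The first is "At least one case in each cohort is required to perform unadjusted and adjusted analyses". The second is "If total counts from the two groups is less than 5, then no adjusted analysis will be performed"; SAP 3.2.4, step 5, repeats the second but not the first.

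The detection rule follows in the same paragraph: "An elevated risk will be detected if the lower limit of the 95% CI for the adjusted relative risk is above 1". SAP 4.5 takes up from there. For a secondary endpoint, investigation begins when the "secondary endpoint analysis detects an elevated risk, further exploration of the data will be completed".

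One output does not depend on the zero-cell rule: "We will calculate crude incidence and 95% CI for each secondary endpoint for the exposed and unexposed cohorts". Table Shell 5 prints the counts for the two cohorts side by side, with a Wald 95% interval for the RR. No decision is attached to the crude incidences. The Wilson interval in SAP 4.4 serves only the single-arm group vaccinated before week 27. No exact, penalised or profile-likelihood method is given for a comparison with an empty cell.

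**The concern.** Read together, these sentences form a closed chain. With no unexposed case there is no RR. With no RR there is no lower limit, so nothing is detected and SAP 4.5 does not start. The number of exposed cases plays no part.

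The rule is therefore non-monotonic. Taking away the single unexposed case from a split that signals makes the contrast stronger but switches detection off. For an analysis meant to find signals, this falls on the most lopsided split the data can show. Whether a cluster seen only in vaccinated women is followed up would then depend on a decision made after seeing the data.

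**Working it through.** **Plan's own figure.** The SAP states no power or detection figure for secondary endpoints. Its one computed figure, 95.7% power for a primary endpoint (SAP 3.3), reproduces. With 15,000 per cohort, 1% against 1.25%, margin 2 and one-sided 0.625%, the score test with constrained null variance gives (0.0075 − 2.498 × 0.001723)/0.001861 ≈ 1.72, a power of 95.7%. The present point does not touch it.

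**Inputs.** Cohorts are matched 1:1 with about 15,000 women each (SAP 3.2.1 and 3.3). The test is two-sided at 5% (SAP 2.2 and 4.3). Background rates of secondary endpoints are not in the documents and are varied below as assumptions.

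**Step 1: when would a zero cell be informative?** With equal denominators and RR = 1, each case falls in either cohort with probability 0.5. For x against 0:

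- two-sided exact p = 2 × 0.5^x
- lower limit for the exposed share, pL = 0.025^(1/x)
- lower limit for the RR = pL/(1 − pL)

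| Exposed vs unexposed | p | Exact lower limit of RR | SAP 4.3 |
|---|---|---|---|
| 5 vs 0 | 0.063 | 0.92 | no analysis |
| 6 vs 0 | 0.031 | 1.18 | no analysis |
| 8 vs 0 | 0.008 | 1.71 | no analysis |
| 10 vs 0 | 0.002 | 2.24 | no analysis |

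At 5 against 0 or fewer, the exact method would not flag either. By that standard the rule costs a detection only from 6 against 0 upward.

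**Step 2: the neighbouring split.** As a stand-in for the adjusted model, take the unadjusted Wald limit (x/y) × exp(−1.96 × √(1/x + 1/y)).

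- 8 vs 1: 8 × exp(−1.96 × √1.125) = 1.001, which just signals.
- 9 vs 1: 1.14, which signals.
- 8, 10 or 20 vs 0: cannot signal.

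**Step 3: how often would this happen?** Let λ be the expected number of unexposed cases, with independent Poisson counts. The chance of landing in the gap is exp(−λ) × P(Poisson(RR × λ) ≥ 6). Detection under the present rule is computed with the Wald stand-in, at least one unexposed case and at least 5 cases in total.

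| λ (per 100,000) | True RR | Chance of 0 unexposed and ≥ 6 exposed | Detection under SAP rule |
|---|---|---|---|
| 0.5 (3.3) | 10 | 23.3% | 4.3% |
| 1 (6.7) | 2 | 0.6% | not computed |
| 1 (6.7) | 3 | 3.1% | 0.5% |
| 1 (6.7) | 5 | 14.1% | 5.6% |
| 1 (6.7) | 10 | 34.3% | 41.6% |
| 2 (13.3) | 2 | 2.9% | not computed |
| 2 (13.3) | 5 | 12.6% | 45.7% |
| 3 (20.0) | 2 | 2.8% | not computed |
| 3 (20.0) | 5 | 5.0% | 77.1% |

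For example, at λ = 1 and RR 5: 0.368 × 0.384 = 0.141.

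**Step 4: false triggers from closing the gap.** At a true RR of 1 the same formula gives 0.02% per endpoint at λ = 1, 0.22% at λ = 2 and 0.42% at λ = 3.

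**The case against.** The best defence is that nothing is concealed. Counts and crude incidences with intervals appear for each cohort. Potential maternal deaths and anomalies are chart reviewed (protocol 4.2, SAP 3.2.3), and the sponsor receives quarterly event reports (protocol 8.3). Protocol section 7 promises exploration if a safety signal is identified, without tying the word to an adjusted RR. SAP section 7 allows documented departures from the plan. All of this stands. It shows that follow-up is possible, but it supplies no rule that requires it.

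The restriction also has a reason. A log-linear Poisson model has no finite RR estimate with an empty cell, and the SAP acknowledges secular confounding between the 2018–2019 and 2012–2013 cohorts (SAP 5.4). A trigger in these cells would rest on an unadjusted historical contrast. That argues for a distinct label, but not for having no trigger, because SAP 4.5 only opens further exploration.

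A reader might lean on SAP 5.2, which says that "researchers do not want to miss the opportunity to detect potential safety findings". In context, that sentence justifies leaving secondary endpoints unadjusted for multiplicity. It shows the intended direction of caution but makes no commitment about zero cells.

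A reader might also take the chance of zero unexposed cases (37% at 1 expected) as the chance of a missed signal. It is not: at least 6 exposed cases are needed as well, which brings the figure down to those in the second table.

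**Conclusion.** The point holds as a narrow gap in pre-specification. From 6 exposed against 0 unexposed upward, SAP 4.3 and 4.5 as written cannot signal, while less extreme splits such as 8 against 1 can. The gap matters only where about 0 to 3 unexposed cases are expected and the true RR is large. At 1 expected case it runs from 0.6% (RR 2) to 34% (RR 10), and at RR 2 it stays below 3% for 1 to 3 expected cases. These figures rest on assumed background rates, equal denominators, Poisson counts and an unadjusted Wald limit in place of the adjusted model.

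Two stronger readings are not supported. One is that the rule defeats the signal-detection objective or bars any investigation. The counts stay visible and protocol section 7 leaves discretion. The other is that maternal death or particular anomaly classes will fall into the gap. The documents give no rates from which to say so. For anomalies, protocol section 7 also notes that the plausible period is early pregnancy, before this cohort is vaccinated. No primary conclusion is affected. The change is worth making because it is cheap and replaces a post hoc choice with a rule.

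**What to change.** In SAP 4.3, replace the zero-cell sentence with text to this effect: *If one cohort has no case, the unadjusted RR will be given with an exact conditional 95% CI (binomial on the split of cases, using persons or person-time). If its lower limit is above 1, section 4.5 signal investigation applies, and the result is labelled as an unadjusted signal.*

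Add the same trigger to SAP 4.5 and a footnote to Table Shell 5, whose RR column is now headed as Wald. With unequal denominators, the limit pL/(1 − pL) is multiplied by the ratio of unexposed to exposed persons or person-time. With no unexposed case the point estimate is infinite, so the table should show it as not estimable beside the lower limit. At equal denominators the trigger needs at least 6 cases, so it does not disturb the existing rule for totals below 5.

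The cost is a few lines of SAS. The downside is that in these cells the trigger rests on an unadjusted historical comparison, so a few more signals may need review.

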- General study aspects: Subject-level data will be collected for pregnant women and their infants through the EHR. For each individual pregnant woman, follow up will begin on the date they received the Boostrix vaccine, or the index date for the unvaccinated cohort, and will end on the date of disenrollment or the end of pregnancy, whichever came first. Infants born in KPSC hospitals from unvaccinated and vaccinated mothers will be followed for 6 months.

Number of subjects Approximately 15,000 pregnant women vaccinated with Boostrix over a period of approximately one year.

Unexposed pregnant women will be matched 1:1 to the exposed group and will be identified from a historical cohort. We aim to have a total sample size of approximately 30,000 pregnant women.

Endpoint(s)
(amended 12 November 2019)

Primary

Maternal and infant adverse events identified from KPSC's EHR system using the pregnancy episode flowsheet and diagnosis codes:

- Preeclampsia and eclampsia
- Intra-uterine infections such as chorioamnionitis and endometritis
- Small for gestational age (SGA)
- Preterm delivery

Secondary

Maternal and infant adverse events identified from KPSC's EHR system using the pregnancy episode flowsheet, diagnosis codes, procedure codes, or death records:

- ***Transfusion during delivery hospitalization***
- Poor fetal growth
- Stillbirth/fetal death with or without congenital anomalies
- Neonatal death (within 28 days of birth)
- Maternal death (while pregnant or within 42 days of end of pregnancy)
- Placental abruption
- Preterm pre-labor rupture of membranes (PPROM)
- Congenital anomalies (CA) at birth and through 6 months of age overall and by system organ class
- Spontaneous abortion (only for women exposed to Boostrix before the 27th week of gestation)
- Therapeutic abortion (only for women exposed to Boostrix before the 27th week of gestation)

To avoid capture of preexisting conditions, diagnostic codes representing each condition should not appear prior to the index date within the pregnancy under study. With the exception of SGA, preterm delivery, ***and transfusion***, medical records of the potential events will then be reviewed by trained research associates to confirm the diagnosis and to ascertain that it is an incident event. Analyses will be done on chart confirmed incident events.

TABLE OF CONTENTS

	PAGE
SYNOPSIS.....	7
LIST OF ABBREVIATIONS	14
GLOSSARY OF TERMS	16
1. INTRODUCTION.....	18
1.1. Background	18

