For events identified any time after the index date such as intra-uterine infection, we will calculate crude incidence and 95% CI for each adverse event for the exposed and unexposed groups. The incidence of each maternal adverse event during pregnancy will be calculated separately and will consist of the total number of women with the condition in the numerator and the total person time in the denominator. The person-year for a pregnant woman will be the time from the index date to the date of each adverse event, end of the pregnancy, or disenrollment, whichever comes first. The adjusted relative risk with CI will be estimated by a Poisson regression model accounting for the follow-up time with adjustment for potential confounders. If the outcome is common (i.e., incidence > 2%), a Poisson regression model with robust variance estimation will be used to estimate the relative risk. For primary endpoints, a two-sided 98.75% CI will be used for the relative risk with multiple comparison adjustment, while for secondary endpoints a two-sided 95% CI will be used.

Congenital anomalies will be identified at birth and through 6 months of age among infants born in KPSC hospitals. Most congenital anomalies are diagnosed by 6 months of age (35). The prevalence of congenital anomalies (overall, by type, at birth, and through 6 months of age) will be calculated as the number of infants with a congenital anomaly in the numerator and the total number of infants born in KPSC hospitals in the denominator. The proportion of live births without congenital anomalies will be calculated as 1 minus the proportion of live births with congenital anomalies among all KPSC live born infants. The adjusted relative risk with 95% CI will be estimated by a Poisson regression model with adjustment for potential confounders. If the outcome is common (i.e., incidence > 2%), a Poisson regression model with robust variance estimation will be used to estimate the relative risk.

The following table outlines the planned method of analysis by endpoint.

Table 7 Analytic population and statistical methods by endpoint (amended 12 November 2019)

Primary endpoints	Analytic population	Statistical Methods
Preeclampsia and eclampsia	All pregnant women eligible for inclusion/exclusion criteria	Adjusted Poisson regression model accounting for follow up time, with robust variance estimate

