Intra-uterine infections such as chorioamnionitis and endometritis	All pregnant women eligible for inclusion/exclusion criteria	Adjusted Poisson regression model accounting for follow up time, with robust variance estimate
Small for gestational age (SGA)	KPSC live born infant, singleton only**	Adjusted Poisson regression model, with robust variance estimate
Preterm delivery	Pregnant women with live birth, with index (vaccination) date prior to 37 weeks gestation	Adjusted Poisson regression model, with robust variance estimate
Secondary endpoints	Analytic population	Statistical Methods
Transfusion during delivery hospitalization	Pregnant women with delivery hospitalization	Adjusted Poisson regression model
Poor fetal growth	All pregnant women eligible for inclusion/exclusion criteria	Adjusted Poisson regression model accounting for follow up time, with robust variance estimate
Stillbirth/fetal death*	Pregnant women with pregnancy outcome	Adjusted Poisson regression model
Neonatal death (within 28 days of birth)	KPSC live born infants	Adjusted Poisson regression model
Maternal death (while pregnant or within 42 days of end of pregnancy)	All pregnant women eligible for inclusion/exclusion criteria	Adjusted Poisson regression model accounting for follow up time
Placental abruption	All pregnant women eligible for inclusion/exclusion criteria	Adjusted Poisson regression model accounting for follow up time
Preterm pre-labor rupture of membranes (PPROM)	All pregnant women, with index (vaccination) date prior to 37 weeks gestation	Adjusted Poisson regression model accounting for follow up time
Congenital anomalies (CA) at birth and through 6 months of age	KPSC live born infants	Adjusted Poisson regression model, with robust variance estimate if outcome is common
Spontaneous abortion	Pregnant women exposed to Boostrix before the 27th week of gestation	Descriptive analysis (proportion)
Therapeutic abortion	Pregnant women exposed to Boostrix before the 27th week of gestation	Descriptive analysis (proportion)

* Stillbirth/fetal death will be described with or without congenital anomalies separately, but will be analyzed as one outcome.

** There are no well accepted SGA metrics for infants born to pregnant women with multiple gestation.

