Congenital anomalies at birth and through 6 months of age d			N/A			N/A			N/A	N/A
Congenital anomalies of nervous system			N/A			N/A				
Congenital anomalies of eye			N/A			N/A				
Congenital anomalies of ear, face, or neck			N/A			N/A				
Congenital anomalies of cardiovascular system			N/A			N/A				
Congenital anomalies of respiratory system			N/A			N/A				
Clefts			N/A			N/A				
Congenital anomalies of upper gastrointestinal system			N/A			N/A				
Congenital anomalies of lower gastrointestinal system			N/A			N/A				
Congenital anomalies of genital organs			N/A			N/A				
Congenital anomalies of renal system			N/A			N/A				
Congenital anomalies of musculoskeletal system			N/A			N/A				
Congenital anomalies of limb			N/A			N/A				
Congenital anomalies of integument			N/A			N/A				
Other and unspecified congenital anomalies			N/A			N/A				
Number of congenital anomalies (based on body system) per infant			N/A			N/A			N/A	N/A
0			N/A			N/A			N/A	N/A
1			N/A			N/A			N/A	N/A
2			N/A			N/A			N/A	N/A
3			N/A			N/A			N/A	N/A
≥4			N/A			N/A			N/A	N/A

a Identified among all pregnant women eligible for main analysisb Identified among pregnant women with index (vaccination) date prior to 37 weeks gestationc Identified among pregnant women with pregnancy outcomed Identified among pregnant women with delivery hospitalizatione Identified among KPSC live born infantsf Adjusted for covariates XXX (place holder, covariates may differ for each endpoint)g Poisson regression model with robust variance estimate (place holder)

\* N/A=Not Applicable

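### SAP Table 5 and Table Shell 5 leave out the relative risk for overall congenital anomalies that the protocol and the SAP's own text call for

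*SAP*

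**What the plan says.** **Protocol.** The synopsis lists the secondary endpoint as "Congenital anomalies (CA) at birth and through 6 months of age overall and by system organ class". Section 2.2 places CA among the events for superiority testing. In section 6.2.2 the CA paragraph first defines prevalence (overall, by type, at birth and through 6 months) and then states: "The adjusted relative risk with 95% CI will be estimated by a Poisson regression model with adjustment for potential confounders". Table 7 gives an adjusted Poisson model to "Congenital anomalies (CA) at birth and through 6 months of age", with no limit to types.

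**SAP text.** Section 2.2 lists CA under the null hypothesis RR = 1. Table 1 lists overall CA as a secondary endpoint, followed by 14 categories. Section 4.3 gives a general rule for the secondary endpoints, "Unadjusted and adjusted RR with two-sided 95% CI will be estimated comparing the exposed cohort to the unexposed cohort", and a signal rule, "An elevated risk will be detected if the lower limit of the 95% CI for the adjusted relative risk is above 1". Its CA paragraph says "The prevalence of congenital anomalies (overall, by type) will be calculated" and ends with an RR sentence that is not restricted to types.

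**SAP tables.** In Table 5 of section 4.3 the only CA row is "Congenital anomalies (CA) by type". In Table Shell 5 of Appendix A the row "Congenital anomalies at birth and through 6 months of age" has N/A under both the unadjusted and the adjusted RR. The 14 category rows beneath it have those cells open.

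**The concern.** Table 5 and Shell 5 are what an analyst programs from. Read literally, they produce 14 category RRs and none for CA as a whole. The protocol's endpoint then loses its planned comparison without any statement that this was intended.

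The signal rule in SAP 4.3, which feeds the signal investigation in SAP 4.5, works on the lower limit of the adjusted RR. An endpoint with no adjusted RR cannot meet that rule in either direction: it can neither raise a signal nor be shown to have raised none. A reader could work out a crude ratio from the counts in Shell 5, but that is not the adjusted comparison the protocol specifies. An isolated signal in one category would also have to be read without the overall estimate beside it.

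**Working it through.** **Step 1. Side-by-side reading.**

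| Place | Overall CA | RR for overall CA |
|---|---|---|
| Protocol synopsis, endpoints | named, with organ class | not addressed there |
| Protocol 6.2.2, CA paragraph | named for prevalence | adjusted RR, not limited to types |
| Protocol Table 7 | whole endpoint | adjusted Poisson model |
| SAP 2.2 | CA listed | null hypothesis RR = 1 |
| SAP Table 1 | listed, then 14 categories | not addressed there |
| SAP 4.3, general rule | covers secondary endpoints | unadjusted and adjusted RR |
| SAP 4.3, CA paragraph | named for prevalence | RR sentence, not limited to types |
| SAP Table 5 | absent, by type only | none |
| SAP Shell 5 | row present | N/A in both RR cells |

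The CA paragraphs of protocol 6.2.2 and SAP 4.3 have the same structure: overall and by type qualify the prevalence sentence, and an unqualified RR sentence follows. They should be read the same way, so both support an overall RR. The contradiction is therefore between two SAP tables on one side and the protocol plus the SAP's own text on the other.

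**Step 2. Is a reason stated?** None was found. For stillbirth, a footnote to SAP Table 5 says what is only described and what is analyzed as one outcome. CA has no such note. The July 2019 SAP (Final 1.0), reproduced after the current one, has the same row label and the same N/A cells, so the later change from hemorrhage to transfusion does not explain them.

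**Step 3. Size.** The documents give no power figure or prevalence for CA. Their only power figure (95.7%, primary endpoints) does not enter here. Two illustrations show what the omission does and does not cost.

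*No true effect.* Each test signals upward with probability 0.025 (lower limit of a two-sided 95% CI above 1).
- Overall test alone: 2.5%.
- At least one of 14 independent category tests: 1 − 0.975^14 = 29.8%.
- The 14 plus the overall test, simulated with 14 independent, equally sized categories and the overall statistic as their standardized sum (1,000,000 runs): about 30.4%.
- Ceiling if all 15 tests were independent: 1 − 0.975^15 = 31.6%.

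*Uniform true RR of 1.2.* Assumed: n = 15,000 infants per cohort (about one per woman), overall prevalence P between 1% and 5%, 14 independent categories each of prevalence P/14, and an unadjusted Wald test on log RR with SE = √[(1−p)/(np) + (1−1.2p)/(1.2np)]. Power for one test = 1 − Φ(1.96 − ln 1.2/SE). Power for any of 14 = 1 − (1 − category power)^14.

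| Assumed P | One category | Any of 14 | Overall |
|---|---|---|---|
| 1% | 6% | 61% | 38% |
| 2% | 9% | 74% | 65% |
| 3% | 12% | 82% | 83% |
| 4% | 14% | 88% | 92% |
| 5% | 17% | 92% | 97% |

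Which route is more likely to signal depends on a prevalence the documents do not give. A single average category has little power on its own anywhere in this range.

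**The case against.** Four points can be made for the plan.

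- **The SAP text already covers overall CA.** This is right: SAP 2.2, Table 1 and section 4.3 all support an overall RR. It narrows the point to two tables out of step with the text, but those tables still need correcting.
- **The overall row in Shell 5 may be only a heading.** This is possible. Another heading in that shell, for the number of anomalies per infant, also carries N/A, and the extracted shells are visibly misaligned. But overall CA is an endpoint in SAP Table 1, Shell 5 offers no other place for its RR, and the Table 5 row label agrees with the N/A cells.
- **Protocol section 7 speaks of describing CA frequency and urges caution, because the plausible period for development of anomalies is early pregnancy.** That supports modest weight for any CA result. It does not withdraw the RR in protocol 6.2.2 and Table 7, and it applies equally to the 14 category RRs, which are kept.
- **Little is lost.** Crude incidence with a 95% CI is still planned for each secondary endpoint in each cohort, and these analyses only generate hypotheses. This stands and limits the weight of the point.

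A reader might also infer that the SAP breaks its own rule on deviations. The paragraph on analysis deviation in SAP section 7 says departures will be documented and a rationale provided. It does not require the rationale to be printed in the SAP, so the documents show only that no reason is stated.

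**Conclusion.** The contradiction is established from the text alone and rests on no assumption. SAP Table 5 and Shell 5 omit the overall CA relative risk that the protocol specifies and the SAP text supports. If the tables are followed, a named secondary endpoint has no adjusted RR for the signal rule. The consequence is limited to one hypothesis-generating endpoint.

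Two stronger readings are tempting and do not hold. One is that restoring the overall test would cut false signals from about 30% to 2.5%. It would not: the 29.8% belongs to the 14 category tests, which remain, and adding the overall test moves it to about 30.4%. The other is that the omission costs much sensitivity, or that it costs almost none. Neither can be claimed. At a uniform RR of 1.2, any-of-14 is ahead of the overall test at assumed prevalences of 1% and 2%, about level at 3%, and behind at 4% and 5%. Those figures also rest on equal, independent categories.

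The gain from correction is that the protocol's comparison is reported and an isolated category signal can be read against it.

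**What to change.** In SAP Table 5, relabel the CA row as congenital anomalies, overall and by type. In Table Shell 5, open the unadjusted and adjusted RR cells of the overall row. Keep the 14 category RRs as planned. If overall CA is meant to be descriptive only, say so with the reason in SAP 2.2 and 4.3 and align the protocol.

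The cost is one row label, two cells and one added model on data already being collected. No primary analysis and no sample size figure changes.
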